After applying the eligibility criteria, 70 patients were randomly divided into four groups using software (www.random.org) by a blinded researcher who was not otherwise involved in the study according to a standardized procedure. The numbers were placed in dark envelopes and concealed. The envelopes were only opened when the irrigation solution was to be activated. The patients were informed about the study without specifying the group to which they were assigned. All procedures were performed by a single operator with five years of experience ([name]).

CBCT imaging (Planmeca Romexis, Helsinki, Finland) was requested for patients who met the study criteria before the procedure to obtain information about periapical lesion size, proximity to anatomical landmarks, and anatomical variations of the tooth. CBCT images were acquired with a field of view (FOV) of 5×5 cm using ENDO mode, an 85 µm voxel size, 6.3 mA, 90 kV, and 8.7 s.

Clinical procedures

A CONSORT flow diagram outlining the treatment methodology is presented in Figure 1. After the administration of local anesthesia and the placement of a rubber dam, the access cavity was opened with a sterile diamond round bur under water cooling. Each canal was rinsed with 2 mL of sodium hypochlorite and explored with a size 08 K-file (FKG Dentaire, La Chaux-de-Fonds, Switzerland). The working length was determined using an electronic apex locator, Root ZX mini (J. Morita Co., Tokyo, Japan), to be 0.5 mm shorter than a 0.0 reading. The length was confirmed radiographically. After that, progressively larger K-files were passively introduced into the canal until the operator felt the first one to bind at the WL and the next larger one not to reach that position [27]. The first instrument used to bind the canal was recorded for each canal. The crown-down technique was applied with ProTaper Next rotary files (Dentsply Maillefer, Ballaigues, Switzerland) using a torque-controlled endodontic motor (SybronEndo, Glendora, CA, USA) at 300 rpm/2-5.2 Ncm rotation mode according to the manufacturer's instructions. The final instrumentation file was set to 3 sizes larger than the first file used[28]. Between each instrument change, the root canal was irrigated with 5 mL of 2.5% NaOCl (Microvem AF, Istanbul, Turkey) for 1 min. After canal preparation was completed, the final irrigation procedure was carried out with the corresponding irrigation method in each group.

[figure not shown]

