Figure 1. Consolidated Standards of Reporting Trials (CONSORT) flow diagram for patients included in this study.

Control Group: Conventional Syringe Irrigation

A 30-gauge side-vented irrigation needle (Kerr Hawe Sa, Bioggio, Switzerland) was used. The needle was inserted into the canal 1 mm shorter than the working length, and the canal was irrigated with up-and-down movements of 1-2 mm amplitude using the same and constant average pressure. The irrigation protocol was performed with 6 ml of 17% EDTA followed by 6 ml of 2.5% NaOCl for 1 min. Between each cycle, 5 ml of distilled water was used to prevent chemical interactions.

Group 1: Manual Dynamic Activation (MDA)

After the root canal preparation was completed, the final irrigation was started, the main gutta percha cone was positioned 1 mm shorter than the working length, and a 2 mm coronal-apical movement was performed at a speed of 100 strokes/minute for 60 seconds. The irrigation protocol was performed with 6 ml of 17% EDTA followed by 6 ml of 2.5% NaOCl for 1 min. Between each cycle, 5 ml of distilled water was used to prevent chemical interactions.

Group 2: Passive Ultrasonic Irrigation (PUI)

In this group, a noncutting ultrasonic tip (IRRI S 21/25; VDW, Munich, Germany) coupled to an ultrasonic device (DTE S6 Led, Guilin Woodpecker Co., Guilin, Guangxi, China) (mode: E, setting: 6) was used according to the manufacturer's recommendations.

The tip was positioned 2 mm short of the working length without contacting the walls. Continuous irrigation was performed using 2 ml of 17% EDTA followed by 2 ml of 2.5% NaOCl with activation 3 times for 20 seconds. To prevent chemical interactions between NaOCl and EDTA, 5 ml of distilled water was used between each irrigant. In total, 1 min of irrigation activation was carried out.

Group 3: Laser-Activated Irrigation (SWEEPS)

In this group, a 2940 nm Er:YAG laser device (Lightwalker, Fotona, Ljubljana, Slovenia) equipped with a handpiece (H14, Fotona) holding an 8.5 mm long and 600 μ m diameter tapered fiber tip (SWEEPS 600, Fotona) was used for irrigation activation. The device was set to AutoSWEEPS mode with two ultrashort micropulses (25 μ s) continuously varying at 0.3 W, 20 mJ, and 15 Hz. The air and water sprays were turned off.

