A 30-gauge side-perforated irrigation needle (Kerr Hawe Sa, Bioggio, Switzerland) was inserted 1 mm shorter than the working length, and the fiber tip was positioned in the center of the access cavity and fixed in this position. Then, 2 ml of 17% EDTA was activated 3 times for 20 s. The same procedure was repeated with 2 ml of 2.5% NaOCl solution by flushing distilled water between each irrigant as described before.

After the final irrigation procedures, the root canals were dried with 25/.06 paper cones (DiaDent, Heungdeok-gu, Korea), and the cold lateral compaction obturation technique with a root canal sealer (Meta Biomed, Cheongju, Güney, Korea) was used to fill all the canals. Permanent restoration was performed directly with composite resin material (Palfique Estelite, Tokuyama Dental Co., Tokyo, Japan).

Follow-up procedures

For routine follow-up, 2D radiographs were taken at 3, 6, and 9 months, as well as via intraoral examinations. Radiographic healing in both 2D and 3D at baseline and at a follow-up of 1 year was assessed by a calibrated evaluator who was blinded to the allocation group. The teeth were assessed for reported symptoms, sensitivity to palpation and percussion, mobility and probing depth. The presence of failure (intraoral swelling or sinus tract) was recorded.

Healing evaluation: lesion area and volume calculation

Twelve months after the root canal treatment, new CBCT images were taken with the same device (Planmeca Promax 3D Classic device (Planmeca Romexis, Helsinki, Finland)) and the same parameters (85 μ m voxel size, 6.3 mA, 90 kV, 8.7 with FOV area 5x5 cm).

3D lesion volume calculation was performed using ITK SNAP (free software under the GNU General Public License developed by the National Institutes of Health, the US National Institute of Biomedical Imaging and Bioenergy needs, the US National Library of Medicine, the Universities of Pennsylvania and North Carolina, and an independent group of developers) by an oral maxillofacial radiologist with 12+ years of experience.

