The preoperative and 1-year postoperative CBCT images of the patients were measured following the same steps in the ITK-SNAP program. We used the same techniques used by Schloss et al[15]. First, the captured CBCT images were exported in DICOM file format from the Planmeca Romexis software. The exported images were then opened with ITK-SNAP software. Using the highest resolution allowed by the captured CBCT images (0.09 mm), the slice thickness and slice interval were set to 0.09 mm. The ITK-SNAP program includes a semiautomatic segmentation feature, which was utilized. In this feature, automated spherical fillers, or bubbles, as referred to in the program, were placed according to the grayscale of the lesion. Repeated runs were performed until the entire area of the lesion was filled, with the bubbles placed in the lesion area. After the internal area of the lesion was completely filled, the images were evaluated from axial, sagittal, and coronal sections to correct any possible overfilling or underfilling situations due to artifacts from canal filling materials using a manual marker. The volume of the painted area obtained was calculated in mm³ using the program's feature. The evaluation of the tomography images obtained before and after treatment was conducted at one-month intervals. The images were provided to the evaluators in a randomized manner.

The volume data were compared with the preoperative CBCT measurements for each patient. The volume changes were measured, and the long-term outcomes of the procedures were compared.

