Association between the Irrigation-Agitation Techniques and Periapical Healing of Large Periapical Lesions: A Randomized Controlled Trial

Clinical Trial Number: NCT06204887

Date: 16.05.2024

Statistical analysis

Analyses were carried out in the IBM SPSS 25 program. As the first step of the statistical analysis, the normality of the data was checked with the Shapiro–Wilk test. When normality was ensured, the Wilcoxon signed rank test was applied to examine the difference between the means of two dependent groups. ANOVA was used to examine the difference between the means of three or more independent groups. In cases where the data were not normally distributed, the Kruskal–Wallis test was performed. The post hoc Bonferroni correction was used to determine the group or groups that were significantly different.

Pearson's chi-square test was applied to examine the relationships between study groups and sex. The Kruskal–Wallis test was applied to examine the differences between the average ages of the participants in the study groups. Spearman correlations were used to control for the relationships between age and lesion volume measurements obtained at different times and from different study groups. To compare lesion volume measurements according to study group at different measurement times, ANOVA and the Kruskal–Wallis test were applied. Bonferroni correction were performed to compare the groups. Wilcoxon signed rank tests were used to compare lesion volume measurements according to different measurement times in the study groups.

For comparisons of lesion volume measurements at different measurement times in the study groups, assumptions were checked, and Wilcoxon signed-rank tests were used. Analyses were performed with the IBM SPSS 25 (SPSS Inc., Chicago, IL) program. The Pearson chi-square test was used to examine the relationships between study groups and sex. The Spearman correlation test was used to assess the relationships between lesion volume measurements obtained at different times and study group and age.

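### The SAP's only tests of volume change are before-versus-after tests within each arm; these cannot show a technique effect and should be made secondary to the planned between-arm comparison

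*SAP*

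**What the plan says.** **Within-arm tests.** The Statistical analysis section of the SAP states that "Wilcoxon signed rank tests were used to compare lesion volume measurements according to different measurement times in the study groups". Its last paragraph repeats this: "For comparisons of lesion volume measurements at different measurement times in the study groups, assumptions were checked, and Wilcoxon signed-rank tests were used". Volume comes from CBCT, which the Protocol schedules before treatment and at 12 months. This amounts to one before-versus-12-month test per arm, four in all.

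**Between-arm tests.** The same section also says: "To compare lesion volume measurements according to study group at different measurement times, ANOVA and the Kruskal–Wallis test were applied", and then "Bonferroni correction were performed to compare the groups". These tests concern the volume at a given time. No between-arm test of the change in volume and no baseline-adjusted model is named.

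**Change in volume.** The Protocol, under Healing evaluation, says that "The volume data were compared with the preoperative CBCT measurements for each patient". It adds that volume changes were measured and that the procedures' outcomes were compared, without naming a test.

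**What the arms share.** Access, preparation and intermediate NaOCl irrigation are described once for all patients. Then, "After canal preparation was completed, the final irrigation procedure was carried out with the corresponding irrigation method in each group". The comparator is headed "Control Group: Conventional Syringe Irrigation" and uses the same two irrigants, EDTA and NaOCl. Of the obturation technique the Protocol says that it "was used to fill all the canals. Permanent restoration was performed directly with composite resin material". There is no untreated arm.

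**The concern.** Lesions may be expected to shrink over 12 months after root canal treatment, whichever technique is used for the final irrigation. The change seen in one arm is the sum of healing common to all arms, any effect of that arm's technique, and measurement error. Testing that sum against zero cannot separate its parts. Randomisation protects only the contrast between arms.

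Two misreadings are possible. If all four within-arm tests are significant, this can be reported as success for every technique, although it says nothing about technique. If some are significant and others are not, the pattern looks like a difference between techniques, although differing p-values are not a test of a difference. The SAP leaves room for both. It names no primary analysis, does not rank the two kinds of test, and offers no other test to a reader who looks for evidence on change.

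**Working it through.** The documents give no figure on this point to reproduce. The question is how often identical arms would yield a misleading or uninformative set of within-arm results.

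**Inputs**
- Four arms and 14 patients per arm (Protocol, Sample size calculation).
- 70 patients randomised (Protocol, Patient Recruitment and Randomization): 70 / 4 = 17.5 per arm, so n = 17 is also shown.
- Type 1 error 0.05 (Protocol); two-sided testing is assumed because sidedness is not stated.
- d, the mean paired change divided by the SD of the paired change. The documents give no volume data, so d is an assumption, shown over a range. It is not the effect size of 0.51 in the sample size section.

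**Method.** Every arm has the same true d, so there is no technique effect. Paired differences are drawn from a normal distribution, and a Wilcoxon signed-rank test at 0.05 is applied in each arm. With per-arm power p and independent arms:
- P(all four significant) = p^4
- P(split: at least one significant and one not) = 1 − p^4 − (1 − p)^4

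**Results, n = 14.** Power comes from 4,000 samples; the last column is a repeat with 20,000 samples per cell.

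| d | p | p^4 | (1 − p)^4 | Split | Repeat |
|---|---|---|---|---|---|
| 0.5 | 0.395 | 0.0243 | 0.1340 | 0.8417 | split 84% |
| 0.7 | 0.665 | 0.1956 | 0.0126 | 0.7918 | split 80% |
| 0.9 | 0.858 | 0.5419 | 0.0004 | 0.4577 | split 46% |
| 1.2 | 0.984 | 0.9375 | 0.0000 | 0.0625 | split 6% |
| 1.5 | 0.999 | 0.9960 | 0.0000 | 0.0040 | all four significant 99.5% |

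Repeat runs differ by about one percentage point. With n = 17 the split probabilities at d = 0.5, 0.7, 0.9 and 1.2 are about 87%, 70%, 28% and 2–3%.

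The most tempting false pattern is a non-significant control with at least one significant active arm. Its probability is (1 − p) × [1 − (1 − p)^3]. At d = 0.5 this is 0.605 × (1 − 0.605^3) = 0.605 × 0.7786 = 0.471. At d = 0.7 and 0.9 it is about 33% and 14%.

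**Second check, on volumes.** Log-normal baseline volumes (log mean 5, log SD 0.8) and identical proportional healing in all arms are assumed, with 14 per arm and 1,000 runs per row.

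| Median shrinkage | SD of log ratio | Within-arm tests significant | Split | Kruskal–Wallis on 12-month volume |
|---|---|---|---|---|
| 30% | 0.5 | 51% | 86% | 5.0% |
| 50% | 0.5 | 96% | 15% | 3.9% |
| 50% | 1.0 | 39% | 87% | 5.7% |
| 70% | 0.5 | 100% | 0% | 3.8% |
| 80% | 1.0 | 98% | 7% | 3.8% |

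Over all ten scenarios run (shrinkage 20% to 80%, SD 0.5 or 1.0), the between-arm Kruskal–Wallis test rejected in about 4–6% of runs, on 12-month volume or on the ratio to baseline. That is the correct behaviour when there is no technique effect. The within-arm rejection rate ran from 6% to 100%, driven by the amount and variability of shared healing.

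**The case against.** The strongest reply is that the comparison which matters is already planned. The SAP has ANOVA or Kruskal–Wallis between arms with Bonferroni correction, and nowhere says that within-arm significance will be used to claim or rank techniques. Whether lesions shrank under each treatment is also a legitimate secondary question, and the Protocol intends to set each patient's volume against the preoperative value. All of this stands. A reader might infer that the plan lacks a between-arm comparison, or that it will judge technique from the within-arm p-values. The documents support neither inference.

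A second reply is that the high split rates need modest or very variable healing. This also stands: with large, consistent shrinkage, splits are rare and the tests are merely uninformative about technique. The documents do not show which situation applies.

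A third reply is that a 95% confidence interval for each arm's change carries nearly the same information as the test. This is true, so dropping the p-values is not enough; the plan also has to say what the within-arm results may be used for.

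What the replies leave open is that the only tests of change are arm-wise, and that nothing in the SAP places them below the randomised contrast.

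**Conclusion.** The concern holds in a limited form and is minor. The within-arm Wilcoxon tests cannot show an effect of technique, and the SAP neither ranks them below its between-arm tests nor names a between-arm analysis of change. Under the assumption of equal true change in all arms, 14 per arm and two-sided 0.05 tests, they mislead often when the standardised change is moderate (splits of about 84% to 46% for d = 0.5 to 0.9). They seldom mislead when it is large (about 6% at d = 1.2), and at d = 1.5 about 99.5% of trials would show four significant arms whether or not technique matters. These figures depend on assumed values of d; the logical point does not.

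A reader might take a within-arm p-value as a contrast of treated with untreated teeth. It is not, because no arm is untreated. Nor does the change show common healing alone, since any technique effect is contained in it too.

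**What to change.** 1. Label the within-arm comparisons descriptive, merge the two sentences that state them, and report each arm's change from baseline to 12 months as an estimate with a 95% confidence interval or as a median and interquartile range.
2. State that conclusions about technique rest only on the randomised between-arm comparison at 12 months, preferably of the change in volume or of 12-month volume adjusted for baseline volume (for example by analysis of covariance, on a transformed scale if needed).
3. State that significance within an arm will not be used to claim or rank technique effects.

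This needs SAP wording and one named between-arm analysis. It needs no new data, because baseline volume is already collected. The cost is the loss of four within-arm p-values as inferential results. The SAP is written in the past tense; if the analyses have already been run, any added between-arm analysis should be reported as added afterwards.
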